2.4.2 Statistical hypothesis, model, and method of analysis

A Poisson distribution will be assumed for the number of participants with composite efficacy failures. Specifically, the number of composite efficacy failure events in group *i* will be assumed to follow a Poisson distribution, i.e., $y_i \sim \text{Poisson}(\mu_i)$, where μ_i is the expected number of events in group *i*, with $\mu_i = \lambda_{i,T} t_{i,T}$, with $t_{i,T}$ being the total on-treatment time in group *i* in years up to T = 12 months, thus incomplete follow-up of participants due to early discontinuation is adjusted for. The follow-up time will be calculated as [min(upper limit of the Month 12 visit window, date of treatment discontinuation, date of lost-to-follow-up) – date of randomization]. The probability of a composite event occurring before *T* can the be derived as $\theta_i = 1 - \exp(-\lambda_{i,T})$.

For the purposes of analysis, time of discontinuation of study drug will be determined by the date of last study drug administration as follows:

- Arm 1: earliest date of discontinuation of study drug (TAC or MMF)
- Arms 2 and 3: CFZ533 study drug discontinuation date + 14 days to account for the dosing interval.

Novartis	For business use only	Page 22
SAP		CCFZ533A2202

The exposure-adjusted treatment difference in composite efficacy failure rates between a CFZ533 arm and Control at Month 12 will then be evaluated as for the primary estimand.

Specifically, a CFZ533 arm will be considered successful if the annualized composite efficacy failure rate difference between this CFZ533 arm and the Control arm is less than 15% with probability greater than 80%:

$$P(\theta_{\rm CFZ533} - \theta_{\rm control} < 0.15 | data) > 0.8$$

The required posterior probabilities will be estimated from simulations of the posterior distributions of $\theta_{CFZ533} - \theta_{control}$ and compared to the threshold for the level of proof. The prior distributions of $\lambda_{i,T}$ will be assumed to be non-informative (specifically, Gamma(0.001, 0.001)). The posterior mean composite efficacy failure rates for each treatment arm and for the difference in mean response rates between CFZ533 treatment arms and control will be presented together with 95% credible intervals.

The posterior probability of the primary decision rule $P(\theta_{\text{CFZ533}} - \theta_{\text{control}} < 0.15 | \text{data})$ will be derived. In addition, posterior probabilities of the composite efficacy failure rates for each treatment arm and the treatment difference being above various thresholds such as 10%, 15%, and 20% will also be presented, i.e. $P(\theta_{\text{CFZ533}} - \theta_{\text{control}} < \theta_0 | \text{data})$, where $\theta_0 = 0.1, 0.12, 0.15$, and 0.2.

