6.6.2 Recommended treatment of adverse events

Acute rejection

For all acute rejection episodes, regardless of initiation of anti-rejection treatment, an allograft biopsy must be performed preferably within 24 hours, latest within 48 hours. Whenever possible, anti-rejection therapy should be postponed until a histological diagnosis of rejection is confirmed. These biopsies will be read by the local pathologist (as well as a central reader up to Month 24 visit), and the histological lesions will be graded according to the Banff criteria (Appendix 3). Determination of the need for treatment will be according to the local pathologist's findings and the investigator's judgement.

All episodes of acute rejection should be treated as per local practice, using for example bolus steroids, increased dose of oral steroids or tacrolimus (for control participants) as first line and anti-T-cell antibody for steroid-resistant rejections.

A steroid-resistant acute rejection episode will be defined when no stabilization and/or no improvement of liver enzymes is seen within five days after initiation of methylprednisolone, when the participant has received at least 3 bolus injections with a minimum of 500 mg/bolus, or a total of 1.5 g of methylprednisolone, or initiation of anti-T-cell antibody treatment after repetitive methylprednisolone.

Whenever possible a re-biopsy should be performed to confirm an ongoing steroid-resistant acute rejection prior to initiating anti-T-cell antibody treatment.

The specific anti-rejection treatment, corticosteroids and anti-T-cell antibody treatment must be recorded on the appropriate CRFs. Increased doses of tacrolimus applied as anti-rejection treatment will be recorded on the corresponding dose administration record CRF page

Participants requiring cyclosporine, azathioprine, everolimus, sirolimus or tacrolimus (if the participant is on a CFZ533 arm) or any other agents for anti-rejection treatment will be discontinued from the randomized study treatment but will be followed until Month 24. Any participant requiring anti-T cell antibody therapy for rejection up to Month 24 should be discontinued from CFZ533 but should continue in the study on standard of care immunosuppression. Participants requiring any of the above treatments for rejection during the extension will be discontinued from the study.

The CFZ533 dose will not be modified and no extra dosing will be administered following a rejection episode.

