12.4.4 Supportive analyses

As a supportive analysis, a Poisson distribution rather than binomial will be applied for the number of subjects with composite failures. Specifically, the number of composite efficacy failure events in group *i* will be assumed to follow a Poisson distribution , i.e., $y_i \sim \text{Poisson}(\mu_i)$, where μ_i is the expected number of events in group *i*, with $\mu_i = \lambda_{i,T} * t_{i,T}$, $t_{i,T}$ being the total follow up time in group *i* in years, thus incomplete follow up of subjects due to early discontinuation is adjusted for. The follow up time will be calculated as [Treatment start date – min (lower limit of the Month 12 visit window, lost-to-follow-up date)].

For the purposes of analysis, time of discontinuation of study drug will be determined by date of last study drug administration as follows:

- Arm 1: earliest date of discontinuation of study drug (TAC or MMF)
- Arms 2 and 3: CFZ533 study drug discontinuation date + 14 days to account for the dosing interval

If a subject discontinues before randomization, the rules of Arm 1 apply.

The exposure-adjusted treatment difference in composite efficacy failure rates between a CFZ533 arm and control at Month 12 will then be evaluated as for the primary endpoint.

In addition, Kaplan-Meier estimates of time to composite efficacy failure and BPAR censored at Month 12 will be respectively constructed and presented graphically. In this analysis, subjects who have not experienced composite efficacy failure, are lost to follow-up, or do not attend the Month 12 visit after treatment discontinuation will be censored with the censoring time defined by the last contact day.

Impact of COVID-19 or any other pandemic on the primary endpoint will be assessed. Details will be presented in SAP.

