2.1 Data analysis general information

Due to the early termination of the study, the analysis plan has been modified and may be different from the Protocol.

The primary analysis will be performed after all participants have completed the Month 12 visit, or prematurely discontinued study before Month 12. These analyses will be performed by a Contract Research Organization, ICON. Interim analyses, detailed in Section 2.13, will be performed also by ICON.

The following general data conventions will apply:

- Cut-off day is defined as the latest study day before or up to which data will be used in the • analysis. Note that safety data collected during the Safety Follow-up period after EOS is reported to Novartis/Safety and will be included in relevant analyses.
- Descriptive statistics will be calculated based on observed values. Missing values will be • presented separately for each parameter or category. Categorical data will be presented as frequencies and percentages. For continuous data, n (sample size), mean, standard deviation, median, 25th and 75th percentiles, minimum, and maximum will be presented.
- BPAR will be based on centrally blinded adjudicated data. All other efficacy • endpoints will also be based on central

lab data.

- AE, SAE, Infection, Serious Infection (including malignancies), CMV information, and • EBV information will be summarized based on all eligible collected events.
- All lab and vital sign tables will include data since baseline (liver Tx) but changes are calculated based on the day of randomization. All summaries are based on central lab data.

Novartis	
SAP	

- Efficacy and liver function analyses are based on all available data including those after study medication discontinuation or as a supportive analysis based only on on-treatment values. Participants are censored for the time-to-event analyses if they do not have an event. For on-treatment analysis, the censoring day is the date of discontinuation of study treatment (defined in Section 2.1.1); for the all-data analysis (regardless of on-treatment or off-treatment), the censoring day is the last contact day.
- Listings will only be provided for variables explicitly indicated in this SAP. Listings will include all available data.

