2.4.1 Primary endpoint

The primary efficacy endpoint is occurrence of composite efficacy failure (BPAR, graft loss, or death) at 12 months post-transplantation based on central pathologist evaluation (graft loss and death will be from local evaluation). The estimand is:

- Population: defined through appropriate inclusion/exclusion criteria to reflect the targeted population.
- Endpoint: composite efficacy failure at Month 12 post-transplantation, defined as BPAR, graft loss, or death.
- Treatment of interest: the randomized treatment, CFZ533 300 mg + MMF, CFZ533 600 mg + MMF, and TAC+MMF, regardless of treatment or study discontinuation, loss to follow-up, ascites-based dosing adjustment, or administration of CS (treatment policy).
- Summary measure: the difference in the proportion of participants with composite efficacy failure in CFZ533 arms at 12 months post-transplantation as compared to control.

BPAR is defined as an acute rejection confirmed by biopsy within 48 hours of the suspected rejection (preferably within 24 hours) with a rejection activity index (RAI) score \geq 3. Events of rejection which were discovered incidentally during the study (e.g., via optional Month 12 biopsy or standard of care biopsy) with no clinical suspicion of acute rejection will not be included in the assessment of the primary endpoint. Note that ascites-based dosing adjustment is not considered a rescue medication because the occurrence of ascites is not due to lack of efficacy. Accordingly, administering CFZ533 to compensate drug loss caused by ascites cannot be considered rescue medication. In addition, this unscheduled administration aims not to result in exposure higher than that seen in participants with no ascites.

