2.4.3 Handling of missing values/censoring/discontinuations

Participants continued to be followed until Month 12 visit, early study drug discontinuation, or lost to follow-up, whichever first. If no event is observed, the partcipant is considered as censored and will still contribute to the analysis as described above.

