5.5.1 Exposure-adjusted incidence rate and 100(1 - α)% confidence interval

Exposure-adjusted incidence rates is presented per 100 participant-years. Participant-years is calculated as a sum of individual participant durations in days divided by 365.25.

It will be assumed that for each of *n* participants in a clinical trial the time t_j , (j = 1, ..., n) to the first occurrence of a certain treatment emergent event is observed, or if the event was not experienced, the (censored) time to the end of the observation period or EOT, whichever occurs earlier. The sequence of first occurrences of an event will be modeled to follow approximately a Poisson process with constant intensity θ . The rate parameter θ will be estimated as $\lambda = D/T$, where $T = \sum_{j=1}^{n} t_j$ and D is the number of participants with at least one event. Conditionally on T, an exact $100(1 - \alpha)\%$ confidence interval for a Poisson variable with parameter θT and observed value D can be obtained based on (Garwood, 1936), from which an exact $100(1 - \alpha)\%$ confidence interval for $\lambda = D/T$ will be derived as follows (Sahai, 1993; Ulm, 1990):

Lower confidence limit
$$L = \frac{0.5\chi_{\frac{\alpha}{2},2D}}{T}$$
 for $D > 0$, and $= 0$ otherwise;

Upper confidence limit $U = \frac{0.5\chi_{1-\frac{\alpha}{2},2D+2}}{T}$.

where $\chi_{\alpha,k}$ is the α -th quantile of the Chi-square distribution with k degrees of freedom.

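### The primary Poisson model does not stop follow-up at the first composite failure, and it does not say whether failures after treatment stop are counted

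*SAP*

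**What the plan says.** SAP 2.4.2 models the number of participants with a composite failure (BPAR, graft loss or death) as Poisson with mean λ·t, where t is defined as "being the total on-treatment time in group" i. The clock is set by this sentence: "The follow-up time will be calculated as [min(upper limit of the Month 12 visit window, date of treatment discontinuation, date of lost-to-follow-up", minus the randomization date. SAP 2.4.3 lists the same three stopping points: "Participants continued to be followed until Month 12 visit, early study drug discontinuation, or lost to follow-up, whichever first". The Poisson formula in Protocol 12.4.4 has no failure date either: "min (lower limit of the Month 12 visit window, lost-to-follow-up date". The rate is converted to a 12-month probability by θ = 1 − exp(−λ). An arm succeeds if the posterior probability that its θ exceeds control by less than 0.15 is above 0.80.

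Other sections do supply what is missing here. SAP 5.4.2 defines the date of composite failure as the earliest component date. SAP 5.5.1 computes exposure-adjusted incidence from the time "to the first occurrence of a certain treatment emergent event is observed".

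On which failures count, the estimand in SAP 2.4.1 applies "regardless of treatment or study discontinuation, loss to follow-up, ascites-based dosing adjustment, or administration of CS (treatment policy", and SAP 2.1 states "Efficacy and liver function analyses are based on all available data including those after study medication discontinuation".

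**The concern.** The conversion 1 − exp(−λ) gives the probability of a first failure only if each participant's time ends at that failure. As written, time ends at failure only when the failure also ends treatment.

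Some failures do: death, graft loss (Protocol 9.1.1), and rejections on a CFZ533 arm that need tacrolimus, anti-T-cell antibody or another listed agent (Protocol 6.6.2). Others need not. Rejection may be treated with steroids, control participants may have tacrolimus increased, and "The CFZ533 dose will not be modified and no extra dosing will be administered following a rejection episode". Those participants remain in the denominator up to the Month 12 limit.

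The dilution is larger in the arm with the higher rate. When CFZ533 is worse than control and failures end treatment about equally often in both arms, the difference shrinks toward zero and the 15-point rule is easier to pass.

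A second mismatch acts the other way. Under a treatment-policy reading, failures after stopping belong in the numerator, but their time is not in the denominator, so rates are inflated. Two programmers could follow the SAP and report different posterior probabilities.

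**Working it through.** **Inputs from the documents.** 48 versus 32 participants, margin 0.15, level of proof 0.80, and Gamma(0.001, 0.001) priors on λ (SAP 2.4.2). Table 3-2 uses Beta(1/3, 1/3) priors (SAP 3.2). The Month 12 limit is Day 358 (SAP 5.1), so T = 357/365.25 = 0.977 years. The expected control rate is 10%.

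**Assumptions.** The documents do not give the share of failures that end treatment, the timing of failures, or the rate of unrelated stopping. These are varied below.

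**1. The plan's own table.** Exact enumeration of two binomials with Beta(1/3, 1/3) posteriors reproduces all 15 rows of Table 3-2 to within about 0.001 (0.15/0.103: 0.7295 against 0.729). The table therefore describes the Beta-binomial rule. No operating characteristics are given for the Poisson rule that is now primary.

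**2. Size of the dilution in closed form** (T = 1 year, no other stopping, constant hazard).
- As written, all failing participants stay on treatment: λ = np/n = p, so θ = 1 − exp(−p). For p = 0.10 and 0.25 this gives 0.095 and 0.221. A true difference of 0.150 becomes 0.126.
- Clock stopped at failure: with hazard h = −ln(1 − p), mean time is p/h, so λ = p/(p/h) = h and θ = p.

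**3. Decision boundary, 9/48 versus 3/32.** The posterior for each λ is Gamma(0.001 + D, 0.001 + time). Failures are taken to fall midway through follow-up on average.

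| Time rule | CFZ533 years | Control years | P(difference < 0.15) | Result |
|---|---|---|---|---|
| As written, no failure ends treatment | 48 × 0.9774 = 46.92 | 32 × 0.9774 = 31.28 | 0.833 | pass |
| As written, half end treatment | (48 − 9 × 0.25) × 0.9774 = 44.72 | (32 − 3 × 0.25) × 0.9774 = 30.54 | 0.805 | pass |
| Clock stopped at failure | (48 − 9 × 0.5) × 0.9774 = 42.52 | (32 − 3 × 0.5) × 0.9774 = 29.81 | 0.772 | fail |
| Beta-binomial | – | – | 0.789 | fail |

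Under the last two rules the largest passing count is 8/48.

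**4. Probability of success**, enumerated over all failure counts with the same time rules.

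| True rates | None end treatment | Half end treatment | Stopped at failure | Beta-binomial |
|---|---|---|---|---|
| 0.25 / 0.10 | 0.277 | 0.240 | 0.196 | 0.217 |
| 0.15 / 0.103 | 0.79 | 0.76 | 0.714 | 0.729 (Table 3-2) |

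At 0.25/0.10 the mean estimated difference is 12.8, 13.8 and 15.0 points for the three Poisson rules. At 0.07/0.20, where CFZ533 is better, the estimate is about −11 points instead of −13, but P(success) is about 0.999 either way.

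**5. When the direction changes** (simulation at 0.25/0.10).
- Unequal stopping, with 80% of CFZ533 and 20% of control failures ending treatment: 0.195 (15.0 points), so no leniency.
- Off-treatment failures counted, 25% unrelated stopping per year: 0.21 as written (14.3 points). Adding only the failure date then gives 0.15 (16.9 points), which overcorrects.
- The two matched versions agree. On-treatment failures over time to failure or stop give 0.200; all failures over time to failure give 0.197.
- Off-treatment failures counted, 30% unrelated stopping on CFZ533 and 15% on control, half of CFZ533 failures ending treatment: 0.14 as written, so the rule becomes stricter.

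**6. Limit of the constant-rate model.** With the clock stopped at failure and every failure at day 60, λ = 0.25/(0.75 + 0.25 × 60/365.25) = 0.316 and θ = 0.271 for a true 0.25.

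**The case against.** The best counter-argument is that the omission is shorthand. SAP 2.4.3 speaks of censoring participants without an event, SAP 5.4.2 supplies a failure date, and SAP 5.5.1 uses time to first occurrence. These are hints, but no text stops the primary clock at failure, and both places that define the clock list its stopping points without it.

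It can also be argued that SAP 2.4.2 and 2.4.3 together imply a purely on-treatment analysis, so that off-treatment failures are simply not counted. That is a reasonable reading, but it contradicts the treatment-policy estimand in 2.4.1 and the general convention in 2.1, and the plan does not settle which governs.

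Several points on size stand:
- The no-stopping figures are an upper bound, because deaths and graft losses do end treatment.
- Protocol 6.6.2 makes stopping after rejection more likely on CFZ533 than on control, and strong asymmetry removes the leniency.
- At the expected 10% control rate the dilution is only about half a point, and 25% lies outside the range of Table 3-2.
- Control time also ends at the earlier of TAC or MMF stop, while CFZ533 time ignores MMF, so the net direction cannot be fixed in advance.
- With early clustering, a failure-stopped θ is somewhat too high, and the formula as written can by chance land closer to the truth.

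Finally, the study was terminated after the interim analysis, and the Kaplan-Meier rates in SAP 2.4.5 do not use this person-time. They are supplementary, however, and do not feed the success rule.

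**Conclusion.** The concern holds. As written, the primary model miscomputes the 12-month failure probability whenever a participant stays on treatment after BPAR, and its numerator and denominator are not tied to the same period. With failures ending treatment equally often in both arms, success at true rates of 25% and 10% has probability between about 0.20 (all end treatment) and 0.277 (none do), against 0.196 with the clock stopped at failure. The pass/fail boundary moves by one participant, from 8/48 to 9/48, against 3/32 in control. The leniency vanishes or reverses with strongly unequal stopping, or if off-treatment failures are counted over on-treatment time. These sizes rest on assumed stopping shares, failure timing and discontinuation rates, because the documents give none. Since the study has ended, what is affected is the reported posterior probabilities and the success statement in the abbreviated report, not a decision to continue. It should be fixed before that report is read.

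**What to change.** 1. Add the date of first composite efficacy failure to the minimum in SAP 2.4.2, and bring 2.4.3 into line.
2. State whether failures after treatment discontinuation count. If they do, as the treatment-policy estimand implies, remove treatment discontinuation from the minimum. If they do not, say so and describe the result as an on-treatment analysis. Steps 1 and 2 must be made together, because step 1 alone can overcorrect.
3. Label Table 3-2 as computed under the Beta-binomial rule, or recompute it under the Poisson rule.
4. Report θ beside the Kaplan-Meier estimate already planned in SAP 2.4.5, because the constant-rate assumption remains.

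The cost is short edits to two sections and one table caption, plus a few lines of code. Failure dates are already derived under SAP 5.4 and no new data are needed. Estimated rates may move up or down depending on the choice in step 2.

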6.5.2 Permitted dose adjustments and interruptions of other study treatment

Tacrolimus

For Control participants (Arm 1) who are unable to tolerate the protocol-specified dosing scheme, dose adjustments and interruptions of tacrolimus are permitted in order to keep the participant on study drug. Temporary interruptions of TAC should not exceed 21 consecutive days.

If TAC is discontinued for more than 21 consecutive days, and the study treatment cannot be maintained, the participant must be permanently discontinued from the randomized study treatment and be managed as per local practice.

MMF

For both CFZ533 and control participants who are unable to tolerate the protocol-specified dosing scheme, dose adjustments and interruptions of MMF are permitted in order to keep the participant on study drug.

The following guidelines must be followed:

• In the event of MMF intolerance (e.g., gastrointestinal disorders, bronchiectasis), temporary dose adjustment or interruption may be necessary. It is recommended to reduce the actual dose by 50%, for approximately 15 consecutive days.

Novartis	Confidential	Page 62 of 136
Amended Clinical Trial Protocol (Version No	. 04 clean)	Protocol No. CCFZ533A2202

• In case of persistent intolerance, MMF can be discontinued and the participant may be switched to other mycophenolates (e.g., Myfortic® mycophenolic acid) and remain in the study on randomized study treatment. Alternatively, MMF may be discontinued completely and participants may remain in the study on randomized study treatment. All dose changes must be recorded on the appropriate CRFs.

Corticosteroids

Corticosteroids will be administered with dosing according to local standard practice in a way that is consistent across all participants enrolled at each site. Corticosteroids may be tapered, as per local standard practice up to a minimal daily dose of 5 mg prednisone (or equivalent dose of another oral corticosteroid) for the first 4 months of treatment. Corticosteroids may then be discontinued (after completion of Month 4 visit) according to investigator discretion. Corticosteroids doses should be recorded on the appropriate CRF.

Management of signs of over-immunosuppression

In case of suspected over-immunosuppression, reducing the CFZ533 dose is not permitted, since under-dosing of CFZ533 may trigger loss of immunosuppression. It is recommended to reduce the MMF dose by 50 % or more.

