2.1.1 General definitions

For the purposes of statistical analysis, "study treatments" are and will be displayed in the outputs as CFZ533 300mg + MMF, CFZ533 600mg + MMF, and TAC + MMF. "Baseline" is defined as the last assessment, including unscheduled assessments, performed prior to liver Tx. All assessments obtained after liver Tx are considered as post-baseline unless otherwise specified. Only centrally adjudicated data will be used for efficacy analyses and laboratory (including vital signs).

In the event that a participant only takes one of the three treatments, the following definitions apply:

- Start of study treatment:
 - a. CFZ533 arms: day of the first loading dose of CFZ533 on Day 8±2 post-LTx.
 - b. Control arm: Day 8 post LTx.
- End of study treatment:
 - a. CFZ533 arms: day of the last dose of CFZ533 +14 days. If a participant in CFZ533 arms discontinues treatment before Day 8±2 (first dose of CFZ533), the rules of control arm apply.
 - b. Control arm: day of the last dose of TAC.

In calculating the duration of treatment, days of permitted interruption of study medication (CFZ, TAC, and MMF) for any reason will be included (see Section 6.5 in the Protocol for details on permitted dose interruption). The entire treatment period is divided into three parts: Treatment Period 1, 2, and 3 (see Section 1.1).

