2.7 Safety analyses

The SAF will be used for safety analyses unless otherwise specified. General safety summaries (tables, figures, etc.) will include only data from the on-treatment period with the exception of baseline data which will also be summarized where appropriate (e.g., change from baseline summaries), unless otherwise specified. For CFZ533 arms, the on-treatment period lasts from the date of first administration of study treatment to 14 days after the date of the last actual administration. For the Control arm, it lasts to the day of the last actual administration of TAC.

Adverse events (AEs) will be presented and summarized for all treatment-emergent events, with a start date after randomization and covering until 14 weeks after the last administration of CFZ533 for CFZ533 arms and 12 weeks after that of TAC for TAC arm. In addition, a separate summary for death will be provided. Malignancies are summarized under SAEs.

All information obtained on adverse events will be displayed by treatment group. The number and percentage of participants with treatment-emergent adverse events and serious adverse events (events started after the first dose of study medication or events present prior to start of treatment but increased in severity based on preferred term) will be summarized in the following ways:

- by treatment, primary system organ class and/or preferred term
- by treatment, primary system organ class, preferred term and/or maximum severity

Separate summaries will be provided for AEs leading to treatment discontinuation.

In addition, the proportion of participants with infections will be summarized as follows:

- Infections by type of infection (viral, fungal, bacterial, others) and severity.
- Serious infections by type of infection (viral, fungal, bacterial, others) and severity.

The incidence rate of infection by type (viral, bacterial, fungal, and others) will be tabulated for each treatment arm. The key safety parameter is serious infections. The number of serious infections will be used to evaluate the stopping rule as outlined in Section 9.1.5 in Protocol.

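### In the primary analysis, stopping MMF ends follow-up for control participants only, although MMF is background therapy in all three arms

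*SAP*

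**What the plan says.** SAP 2.4.2 treats the number of failures in each arm as Poisson, with expectation equal to a rate times total on-treatment time. A participant's time runs from randomization to the earliest of the upper limit of the Month 12 window, treatment discontinuation and loss to follow-up. The discontinuation date is defined by arm:

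- Control: "Arm 1: earliest date of discontinuation of study drug (TAC or MMF").
- CFZ533: "Arms 2 and 3: CFZ533 study drug discontinuation date + 14 days to account for the dosing interval".

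The rate is converted to a 12-month probability. A CFZ533 arm succeeds if the posterior probability of a difference below 0.15 exceeds 0.8.

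Other passages bear on this:

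- SAP 2.4.1 names the randomized treatments as "CFZ533 300 mg + MMF, CFZ533 600 mg + MMF, and TAC+MMF".
- Protocol 6.5.2, writing of CFZ533 and control participants alike, states that "MMF may be discontinued completely and participants may remain in the study on randomized study treatment".
- SAP 2.1.1 defines the end of study treatment as "Control arm: day of the last dose of TAC". SAP 2.7 says of the on-treatment period: "For the Control arm, it lasts to the day of the last actual administration of TAC".
- On the period in which events are observed, SAP 2.4.3 has "Participants continued to be followed until Month 12 visit, early study drug discontinuation, or lost to follow-up, whichever first", while SAP 2.1 has "Efficacy and liver function analyses are based on all available data including those after study medication discontinuation".
- Protocol 12.4.4 carries the same arm-specific definitions, but for a supportive analysis. Its follow-up formula uses only the Month 12 window and the lost-to-follow-up date.

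**The concern.** The same permitted change in background therapy closes the clock in one randomized arm and leaves it open in the other two. A control participant who stops MMF at month 3 and continues TAC is off treatment for the primary endpoint and on treatment for safety. A CFZ533 participant who does the same is on treatment for both. The SAP gives no reason.

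The control rate then varies with MMF tolerability and the CFZ533 rate does not. Two mechanisms pull in opposite directions. Failures may cluster early after transplant; cutting later, low-risk control time then raises the control rate and favours CFZ533. Or risk may rise once MMF is stopped; if later events are dropped, that extra risk is counted only in the CFZ533 arms. Which mechanism dominates depends partly on whether events after the clock stops are counted, and SAP 2.1 and 2.4.3 point different ways on this.

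**Working it through.** **Check of the decision rule.** With binomial outcomes, 48 and 32 participants and Beta(1/3, 1/3) priors, exact enumeration reproduces all 15 cells of SAP Table 3-2 within 0.001 (for example 0.904 at 11% vs 10.3%). The SAP 2.4.2 analysis uses a different model, as follows.

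**Inputs from the documents.** 48 and 32 participants and a control rate of 10% (SAP 3.2); prior Gamma(0.001, 0.001) on each rate, margin 0.15 and threshold 0.8 (SAP 2.4.2); Month 12 window ending at Day 358, so 357 days of follow-up (SAP 5.1).

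**Assumptions, because the documents give none.** The share of controls stopping MMF, the stop time (gamma, shape 2), and the timing of failures: constant hazard, or 70% or 85% of failures in the first 90 days. Stopping is unrelated to risk unless stated.

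**Formula.** With y events in t years, the rate λ has posterior Gamma(0.001 + y, 0.001 + t), and θ = 1 − exp(−λ). Under the SAP formula, time does not end at the event.

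**1. Uncut exposure.** Control: 32 × 357/365.25 = 31.28 years. CFZ533: 48 × 357/365.25 = 46.92 years. At a true control rate of 10%, y/t = 3.2/31.28 = 0.1023, so θ = 1 − exp(−0.1023) = 9.7%.

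**2. Large-sample control θ** (mean stop at month 4, 70% of failures early):

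| Controls stopping MMF | Later events dropped | Later events kept |
|---|---|---|
| 0% | 9.7% | 9.7% |
| 20% | 10.4% | 11.2% |
| 30% | 10.7% | 12.0% |
| 40% | 11.1% | 13.0% |

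Over 20-40% stopping, mean month 3 to 5 and 70-85% early, the rise is 0.6 to 2.0 points if dropped and 1.2 to 3.9 if kept. Under a constant hazard it is about 0 if dropped and 1.2 to 3.8 if kept.

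**3. Probability of success at true 25% vs 10%** (20,000 simulated trials per scenario, standard error about 0.003). With 30% stopping, mean month 4 and 70% early, it is 0.28 uncut, 0.31 dropped and 0.37 kept. With 10% stopping and events dropped it moves from 0.275 to 0.285.

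**4. The other direction.** Let the hazard double after MMF is stopped in both arms (30% stopping, constant base hazard, later events dropped). Control θ falls from 11.3% to 9.7%, and success at realised rates of 23.3% vs 11.8% falls from 0.43 to 0.34. A separate simulation of 6,000 trials, with exposure also ending at the event, used base rates of 11% vs 10% and the same doubling. At 30% stopping it gives success of 0.820 under the SAP rule and 0.869 with a TAC-only rule.

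**5. Single results near the threshold.**

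- 3/32 vs 10/48, uncut: 3/31.28 gives θ = 9.1%, 10/46.92 gives 19.2%, and P(difference < 0.15) = 0.758. If 30% of controls stop at mid follow-up, control time is 31.28 × (1 − 0.15) = 26.59 years. With all events kept, control θ is 10.7% and the probability is 0.802, so failure becomes success.
- 3/32 vs 9/48, uncut: 0.833. If 20% of controls stop at mid follow-up and one event is dropped, control data are 2 events in 31.28 × 0.90 = 28.15 years (θ = 6.9%). The probability is 0.747, so success becomes failure.

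**The case against.** **The rule has a source.** The protocol glossary defines treatment discontinuation as permanently stopping any study drug and counts background therapy as study treatment. On that reading Arm 1 follows the definition and Arms 2 and 3 depart from it. This bears on which repair to choose, but it does not defend the asymmetry, because the glossary definition applies to every arm.

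**The inconsistency is weaker than it looks.** SAP 2.1.1 introduces its definitions with an unclear condition about a participant taking only one of the three treatments, and SAP 2.7 concerns safety. Both points are fair. Still, SAP 2.7 repeats the TAC-only end without that condition, and no passage explains a different rule for efficacy.

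**A larger problem sits above it.** SAP 2.4.1 states a treatment-policy estimand, while 2.4.2 and 2.4.3 stop at drug discontinuation in every arm. Making the MMF rule symmetric does not resolve that. This stands, and it is a separate matter.

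**The numbers are selected.** SAP 2.4.3 suggests that later events are dropped, which is the reading with the smaller effects. The flip to 0.802 is narrow: at 20% stopping the figure is 0.787. If time also ends at the event, taken as midway, exposures are 29.81 and 42.03 years and the probability goes from 0.674 to 0.728, with no flip. The 25% vs 10% scenario lies on the margin. At the planned 11% vs 10.3% (30% stopping, mean month 4, 70% early), a simulation of 1,500 trials gives 0.926 uncut, 0.933 dropped and 0.946 kept. A switch to another mycophenolate may not count as stopping MMF, so the true rate could be low. All of this limits the size; none of it removes the asymmetry.

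**The trial has ended.** The study was terminated after the interim analysis and an abbreviated report is planned. That lowers the stakes to the reported primary result.

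**Conclusion.** The concern holds as a matter of text. The primary analysis uses a different discontinuation rule for MMF in the control arm than in the CFZ533 arms, without explanation and against the SAP's own TAC-only definitions. The protocol precedent does not cover it, because the SAP formula is what brings the discontinuation date into follow-up time and makes this the primary analysis.

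Size and direction are not determined by the documents. They depend on the assumed MMF-stop rate, the timing of failures, the link between stopping and risk, and whether later events count. The effect is about zero in expectation under a constant hazard with later events dropped. It is small at 10% stopping, and a few points in either direction in the less favourable scenarios. Near the threshold that can change the decision; at the planned event rates it rarely would. The change should be made, but it is not critical.

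**What to change.** - In SAP 2.4.2, define control discontinuation as the day of the last TAC dose, as in SAP 2.1.1, so that stopping MMF does not end follow-up in any arm. If MMF is meant to count, apply it in all three arms. Either choice can keep the 14-day dosing-interval allowance for CFZ533, which is not at issue.
- State whether events after the clock stops are counted, and reconcile SAP 2.1 with 2.4.3.
- Record the departure from Protocol 12.4.4 in SAP section 4, which at present declares no changes.
- If the primary analysis is instead brought into line with the treatment-policy estimand, make the same correction in any on-treatment analysis that is kept.

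The cost is one bullet and one sentence in SAP 2.4.2 and one line in section 4. Stop dates for CFZ533, MMF and TAC are already in the dosage administration records (Protocol 9.1.1).
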